9.3 Outcome Measures

9.3.1 Primary outcome measure

Primary Outcome: OMWQ-HN score at week 6 following start of LLLT treatment.

9.3.2 Secondary outcome measures:

- OMWQ-HN and WHO mucositis scores collected at baseline and weekly during weeks 1-6 of treatment.
- Long term reported health related quality of life as measured by EORTC QLQ C30 (version 3.0),
 EORTC QLQ C30/H&N 35 (EORTC QOL Module for Head and Neck Cancer) and the EQ-5D-5L at baseline, week 6, month 4 and month 14, and MDADI at baseline, week 6, month 4 and month 14.
- Nutritional Parameters as measured by Performance Status Scale's (PSS-HN) collected weekly
 at baseline, weeks 1-6, month 4 and month 14. Recording of weekly weight changes from
 baseline during treatment, the quantity of enteral nutrition consumed, number of days of
 feeding tube in situ.
- Changes in swallowing function measured by the timed water swallow test collected at baseline, week 6 of LLLT month 4 and month 14.
- Pain outcomes as measured by use of analgesics/ topical treatment and pain domain of EQ 5D-5L and OMWQ-HN at randomisation and weekly to week 6 during treatment.

 Safety, specifically adverse events attributed to LLLT and clinical complications notably number of days as inpatient hospital admissions and interruptions in CRT treatment (recorded weekly 1-6 during treatment).

• Clinical outcomes specifically patient survival, quality-adjusted survival recurrence and persistence of disease at 14 months.

Economic outcomes:

- Incremental cost per change in OMWQ-HN score recorded between baseline and at week 6 of therapy and incremental cost per QALY over 14 months
- Quality-adjusted life years based upon EQ-5D-5L [14] and EORTC-8D [15] utility scores measured at baseline, week 6 and 4 and 14 months
- Costs associated with treatment (weeks 0-6) will be collected weekly via the eCRFs
 (e.g. adverse events and use of analgesics)
- Health care utilisation based on responses to Health Utilisation Questionnaire administered at 4 and 14 months (assessing: visits to the GP/walk-in clinic/A&E etc.)
- Participant and family costs collected via the Time and Travel Questionnaire administered at 14 months
- Total costs of LLLT and sham LLLT measured at 4 and 14 months, from the perspective of the NHS and personal and social services to participants and families

Qualitative outcomes as identified through:

- Observations of training
- Interviews with health professionals delivering LLLT
- Interviews with other relevant members of the head and neck cancer team
- Audio-recording of recruitment discussions

10. TRIAL DESIGN

This is a multi-centre (up to 10 regional cancer centres in England, Scotland and Wales), 2 arm parallel group, blinded randomised controlled trial (RCT). LiTEFORM aims to evaluate the effectiveness and efficiency of LLLT in reducing the severity and impact of OM in adult patients receiving (C)RT for HNC.

Patients will be randomised 1:1 to receive standard care plus LLLT (n=190) verses standard care plus sham LLLT (n=190). Both arms will receive the current standard care which includes optimisation of

good oral hygiene, hydration and use of analgesia, topical analgesics and coating gels for pain management. Treatment allocation will be stratified by two factors: 1. planned treatment (radiotherapy alone or chemo-radiotherapy 2. Unilateral or bilateral radiotherapy fields.

As part of the qualitative evaluation, a sample of patients who have consented or declined the main trial will be invited to take part in a telephone interview (n≤36). Staff at participating sites involved in trial recruitment/patient care, staff delivering LLLT, and other relevant members of the HNC team, will also be invited to take part in interviews. There will be observations of trial training and audio-recording of recruitment discussions (approximately 6-8 per site selected for analysis).

Pilot Study:

LiTEFORM includes a 9 month pilot phase (7 sites) with robust progression criteria to the full RCT (an additional up to 3 sites with a total of up to 10 sites). The pilot will look at all aspects of feasibility, safety and efficiency for LiTEFORM, with a qualitative process and economic evaluation. All 7 pilot sites will be set up as quickly as is possible during the pilot phase.

Progression Criteria:

Month 1 - Contractual start date and month funding starts from is 01 January 2017.

- Site set-up to be complete for 4 pilot centres by month 4 post funding, including the training of a minimum of 2 nurses or delegated staff to deliver LLLT in each centre to a competent level to ensure no gaps due to leave breaks etc. The second phase of an additional 3 centres to be set up by month 6.
- First 4 pilot centres recruiting on average 1.5 patients per month for the first 4 months post funding.
- First 4 sites recruiting at full rate, on average 2 patients per month from months 5 to 9 Post funding
- Additional 3 sites recruiting on average 1.5 per month during months 3 and 4.
- Additional 3 sites recruiting on average 2 patients per month during months 5-9.
- Completion of OMWQ- HN at week 6 in at least 80% of randomised patients
- Minumum of 100 patients recruited and randomized into LiTEFORM by completion of the pilot.

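### The pilot's early recruitment targets and its 100-patient minimum assume sites recruit almost from the funding start, which the site set-up dates beside them do not require

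*Protocol*

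**What the plan says.** All of this is in protocol section 10, under the pilot study and its progression criteria.

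- Clock: "Month 1 - Contractual start date and month funding starts from is 01 January 2017".
- Set-up: "Site set-up to be complete for 4 pilot centres by month 4 post funding", and "The second phase of an additional 3 centres to be set up by month 6". The same section says that all seven sites will be set up without delay.
- Early recruitment: "First 4 pilot centres recruiting on average 1.5 patients per month for the first 4 months post funding", and "Additional 3 sites recruiting on average 1.5 per month during months 3 and 4".
- Later recruitment: both groups of sites are to average 2 patients per month in months 5 to 9.
- Total: "Minumum of 100 patients recruited and randomized into LiTEFORM by completion of the pilot".
- Data completeness: "Completion of OMWQ- HN at week 6 in at least 80% of randomised patients".

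The pilot is described in these words: "LiTEFORM includes a 9 month pilot phase (7 sites) with robust progression criteria to the full RCT". Section 11 gives 24 months of recruitment, 9 of them pilot, and a final report at month 47.

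**The concern.** Set-up and recruitment sit on one clock but do not fit together. The first four centres are asked to recruit through months 1 to 4, although their set-up may properly finish as late as month 4. The other three are asked to recruit in months 3 and 4, although their set-up is due only by month 6. A site cannot recruit before it is set up: set-up includes training staff to deliver the laser, and section 21.4 bars enrolment before local NHS permission.

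These criteria inform the decision to proceed to the full trial. If the minimum presumes an earlier opening than the set-up criteria require, a shortfall could mean slow recruitment or merely set-up on schedule, and the total alone does not say which. The completeness criterion has a related weakness. Its denominator is everyone randomised, including patients too recent to have reached week 6.

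**Working it through.** **1. The plan's own figure.** Rates and months are those in section 10, read as per centre.

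| Sites | Funding months | Rate | Patients |
|---|---|---|---|
| First four | 1 to 4 | 1.5 | 4 × 1.5 × 4 = 24 |
| First four | 5 to 9 | 2 | 4 × 2 × 5 = 40 |
| Additional three | 3 to 4 | 1.5 | 3 × 1.5 × 2 = 9 |
| Additional three | 5 to 9 | 2 | 3 × 2 × 5 = 30 |
| Total | | | **103** |

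This reproduces the minimum of 100 with 3 to spare, which is half a month's recruitment at the first four centres (4 × 1.5 × 0.5 = 3). Reading the rates as totals for each group of sites gives 1.5 × 4 + 2 × 5 + 1.5 × 2 + 2 × 5 = 29, so the per-centre reading must be the intended one.

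**2. The same rates with other opening dates,** counted to month 9. The rate is 1.5 up to month 4 and 2 afterwards, unless noted.

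| First recruiting month: first four / additional three | Calculation | Total |
|---|---|---|
| 5 / 7 (set-up done at the end of months 4 and 6) | 4×2×5 + 3×2×3 | **58** |
| 4 / 6 (recruiting throughout those months) | 4×1.5×1 + 4×2×5 + 3×2×4 | **70** |
| 4 / 6, at 2 per month from opening | 4×2×6 + 3×2×4 | **72** |
| 3 / 3 | 12 + 40 + 9 + 30 | 91 |
| 2 / 3 | 18 + 40 + 9 + 30 | 97 |
| 1 / 4 | 24 + 40 + 4.5 + 30 | 98.5 |
| 2 / 2 | 18 + 40 + 13.5 + 30 | 101.5 |
| 1 / 3 | 24 + 40 + 9 + 30 | 103 |

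The drop from 103 to 58 is 45 patients: 24 + 9 = 33 from months 1 to 4, and 3 × 2 × 2 = 12 from the additional sites in months 5 and 6.

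**3. Rate needed to reach 100 from the latest dates.** Opening at the end of months 4 and 6 leaves 4×5 + 3×3 = 29 site-months, so 100/29 = 3.4 patients per site-month. Recruiting throughout months 4 and 6 leaves 4×6 + 3×4 = 36 site-months, so 100/36 = 2.8. The stated full rate is 2.

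**4. Counting from opening instead.** Let recruitment month 1 be the opening of the first four centres, with the other three starting in recruitment month 3: 4 × (1.5×4 + 2×5) + 3 × (1.5×2 + 2×5) = 64 + 39 = 103. The two-month gap between the set-up dates (4 and 6) equals the gap between the recruitment starts (1 and 3). This suggests that the rates were planned in months of recruitment and then labelled by funding month. That is an inference; the text does not say so.

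**5. The 80% criterion.** Assumption: it is assessed at pilot end, since no date is stated. Recruitment is then 7 × 2 = 14 per month. Patients randomised in the last 6 weeks number 14 × 6/4.33 = 19.4. For the last 8 weeks, allowing the two extra weeks that section 13.6 gives for the form, the number is 14 × 8/4.33 = 25.9. Out of 103, the highest possible completion is 83.6/103 = 81% and 77.1/103 = 75%. If the 10 to 15% dropout expected in section 13.8 applied in full by week 6 (a further assumption), completion would be about 0.75 × 0.85 = 64% to 0.81 × 0.90 = 73%.

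**The case against.** Months 4 and 6 are deadlines, and the protocol intends to open sites as fast as it can. A pilot that opens earlier also satisfies them and could reach 100. This stands. A reader might infer that every pilot meeting the set-up dates must fail, and the documents do not support that: totals compatible with the set-up wording run from 58 up to and beyond 100. What survives is that 100 needs opening almost at the funding start, which the set-up criteria do not ask for.

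The rates are required averages, not ceilings. True, but from the latest dates the shortfall takes 1.4 to 1.7 times the full rate to close (2.8/2 and 3.4/2).

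The go/no-go decision is not emptied of meaning. The month 5 to 9 rate for the first four centres is consistent with their set-up date and still informative, and section 10 does not say that one missed criterion stops the trial.

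A reader might also infer that 24 months cannot deliver 380. That needs a main-phase rate, which the protocol never gives, and all ten sites, where it says up to ten. Section 11 also states the 24 months as recruitment time without tying them to funding.

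On completeness, the assessment date is an assumption, and the ceiling of 75 to 81% straddles 80%, so failure is not shown before dropout.

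Finally, this is protocol version 2.1, while the SAP cites version 4.0, which is not available here. Whether the criteria were later changed is unknown. SAP section 2.6 reports closure with 87 randomised for lack of recruitment; nothing there links the closure to this inconsistency.

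**Conclusion.** The point holds as an internal inconsistency of timing. The rates and the minimum agree with each other (103 against 100) but not with the set-up dates in the same list. With opening on the latest permitted dates and the stated per-centre rates, the pilot reaches about 58 by month 9, or 70 to 72 if sites recruit throughout months 4 and 6. It would then pass on set-up and fail on the total and on some or all of the early-month targets. I have not assumed a slow start tied to each site's opening, because the protocol attaches the lower rate to calendar months.

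The completeness denominator is a smaller, conditional point: it bites if the criterion is assessed at pilot end. The main sample size of 152 evaluable and 190 recruited per arm is unaffected.

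**What to change.** Define one time origin for all four recruitment bullets: for example, recruitment month 1 is the opening of the first four centres, the additional three open by recruitment month 3, and the 9-month pilot runs from that date. The stated rates then give 103 and the minimum of 100 can stand. Deleting the reference to funding is not enough, because the two bullets on the additional sites do not contain it and would still inherit the month 1 definition.

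Alternatively, keep the funding clock and restate the early-month criteria and the minimum to what the set-up dates deliver, about 58 to 72.

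In either case, assess the 80% criterion only in randomised patients whose week-6 window has closed.

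The edit is a few lines, but the first option costs time. If the first four centres open at the end of month 4, the pilot ends in funding month 13 instead of 9, so the decision falls about four months later. If the 24-month recruitment window also runs from opening (May 2017 to April 2019), adding 6 weeks and 14 months puts last visits at about mid-August 2020. The database lock that section 13.10 expects around July 2020 must then move, and less time is left for analysis before month 47 (November 2020).

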11. TRIAL SETTING

This trial will take place in up to 10 HNC treatment centres in England, Scotland and Wales. Patients will be approached about the trial at the time they are consented for their (C)RT.

Recruitment will take place over 24 months (9 months pilot, 15 months RCT) with trial completion at 47 months (submission of final report).

12. ELIGIBILITY CRITERIA

12.1 Inclusion Criteria

- Adults aged ≥ 18 years diagnosed with HNC
- Capacity to provide informed written consent
- Histological diagnosis of squamous cell carcinoma of the oral cavity, oropharynx, nasopharynx, larynx, hypopharynx or unknown squamous cell primary of head and neck origin histologically confirmed
- (C)RT patients discussed in a Head and Neck MDT meeting and deemed medically fit for an
 agreed treatment plan for primary or adjuvant radiotherapy ± concurrent or induction
 chemotherapy (cisplatin or cetuximab)
- Patients planned to receive a minimum of 60Gy to a defined clinical target volume in the oral cavity or oropharynx, or neck levels Ia/b as defined by the current RTOG criteria

12.2 Exclusion Criteria

- Known to be pregnant or planning to become pregnant within the trial treatment period
- Photosensitive Epilepsy
- Primary Parotid tumours
- Previous radiotherapy for HNC
- Current/ongoing OM and trismus limiting laser access for treatment
- Patients who are experiencing active heavy tumour bleeding from the mouth (haemorrhage)
- Patients for whom the MDT recommend short course palliative radiotherapy
- Patients on immune suppressant drugs (except low dose steroids)
- Participation in other trials assessing different treatments for OM

Unable to provide written informed consent

13. TRIAL PROCEDURES

13.1 Recruitment

13.1.1 Patient Identification and Pre-Screening

Patients will be identified as potentially eligible by staff with delegated responsibility following head and neck multidisciplinary team decision making. Patients will be informed about LiTEFORM when they attend clinic to consent for their radiotherapy and/or chemotherapy. This initial clinic appointment with the oncology team will cover the standard information about the side effects of their treatment and patients will be consented at this stage to undergo (C)RT (this consent process relates to the treatment and is entirely separate to the trial consent process). LiTEFORM will not be discussed in any great detail at this time. A lot of information will be given to patients by the oncologists and they will likely receive standard MacMillan information on (C)RT side effects from their clinical nurse specialist. The patient will be told how the LiTEFORM trial relates to these side effects and all patients who are potentially eligible will be given a Patient Information Sheet to read and consider in their own time.

13.1.2 Screening and Consent

Potential participants will be screened against the inclusion and exclusion criteria using the clinic lists and patient medical notes.

All patients who were given a LiTEFORM Patient Information Sheet will be re-approached about the trial when they attend the oncology clinic for their (C)RT planning appointments.

Informed consent discussions will be undertaken by a delegated member of the research team (as per the delegation log) with the opportunity for the patient to ask any questions and discuss the trial in more detail. All patients will be given a minimum of 48 hours after receiving the Patient Information Sheet to decide whether or not they would like to take part.

After eligibility has been confirmed, full written informed consent will be provided by signing, dating and initialling the consent form, which will be witnessed by a member of the research team who has documented and delegated responsibility so to do. The original signed consent forms will be retained in the Investigator Site File (ISF), with a copy filed in the clinical notes and a copy provided to the patient.

Qualitative sub-study:

Audio-recording: Verbal consent will be obtained to audio-record the recruitment and trial consent discussion with patients, at the start of the discussion. All those present must give verbal consent, including friends and family. If anyone declines then the discussion will continue without being recorded. All those present must provide written informed consent for the audio-recording at the end of the discussion or it will be deleted immediately. Consent can be withdrawn at any point during the discussion.

All those present who gave written informed consent for the discussion to be audio-recorded will be given a follow up information sheet to explain how they can contact the research team or qualitative researcher should they change their mind about the recording.

Patient Interviews: During the trial consent discussion all patients will be asked if they can be contacted about a telephone interview. All patients will be invited to take part, including those who declined taking part in the randomised trial. Not all patients who consent to be contacted about an interview will be contacted, and they may be contacted either 1-2 weeks after the recruitment discussion, and at approximately month 4 or month 14. There will be no more than 2 interviews per patient.

Patients will be given an Interview Patient Information Sheet to take away with them for consideration and asked for written consent to be contacted, allowing their details to be passed securely to the research team. The qualitative researcher will telephone the patient and, if the patient agrees, arrange a convenient time and date to conduct the interview. Verbal consent will be obtained at the very start of the call, including to audio-record the interview. The recorder will be switched on and the research will go through the consent form questions before the interview starts.

Staff Interviews: Interviews with health professionals will take place throughout the trial duration using purposeful sampling. Most interviews will be done via telephone, although some may be done face to face (for example to co-incide with a SIV observation). Taking part will be optional. There will be no more than 2 interviews per staff member. For all telephone interviews, the same process regarding obtaining verbal consent will be followed as for the patient interviews. Written informed consent will be obtained for all face to face staff interviews.

Observations: Written informed consent will be obtained from all staff present at the launch event site initiation visits and training sessions, at the start of the visit. If an individual does not wish to take part in an observation of a group activity, the researcher will not make any notes about that person or their involvement in the group. Anyone present can ask that observations are not undertaken at

any particular time and for any individual situation where, in their judgement, this course of action is not considered appropriate.

13.2 Randomisation

Patients will be randomised to receive standard care plus LLLT or standard care plus sham LLLT on a 1:1 basis using a method of random permuted blocks of concealed variable block size and stratified by 1. planned treatment (radiotherapy alone or chemo-radiotherapy 2. Unilateral or bilateral radiotherapy fields. To ensure concealment of allocation, patients will be centrally randomised by the Newcastle Clinical Trials Unit using a secure web-based system. It provides ease of operation with inbuilt validation/plausibility checks at time of data entry. The PI at site or an individual with delegate authority will access the web based randomisation system and enter in the required information. The system will return a unique patient trial number and the randomised treatment allocation which corresponds to one of the two settings on the laser machine. A telephone and/or email randomisation service will be used should the web based system be unavailable for any reason.

13.3 Blinding

The equipment manufacturer has modified the laser device to deliver the sham treatment. The protective glasses block the red colour of the light and prevent staff delivering the LLLT from knowing if the machine is delivering the sham output or active laser. Staff will operate the machine following the Standard Operating Procedure for the trial and laser safety rules, and the machine will be switched off prior to removal of all safety glasses.

LLLT will be delivered in a locked room with all reflective surfaces covered or absent. The machine will emit audible beeps when delivering both the sham and the intervention. All staff trained to deliver LLLLT will wear protective eye glasses as per the laser instructions for use (which comply with EU legal requirements).

The sham LLLT has built in additional resistors in the head of the probe to create warmth as if it was delivering the laser therapy. This reduces the risk of un-blinding of the patient and staff delivering LLLT.

The trial doctors and nurses administering the assessment tools for data collection and the researcher conducting the qualitative interviews will be unaware of which treatment each patient has received. The staff taking the WHO mucositis score will take an intraoral photograph at the time of their final score, which can be anonymised for independent fully blinded evaluation by another member of the research team.

All of the Trial Management Team will be unaware of which patients have received which treatment except the staff performing the randomisation.

13.4 Un-blinding

Only delegated members of the Newcastle Clinical Trials Unit will be able to un-blind a participant and only when deemed as necessary. Un-blinding may be needed for safety reasons that may influence the future clinical care of the patient. For example accidentally shining the laser in the eye of a participant or staff members during treatment, which would require further examination by an ophthalmologist within 24 hours.

If a patient or staff members becomes convinced they know which treatment they are receiving, this will be recorded along with any reasons provided. However, unless there are safety concerns for the person they will not be un-blinded in this case.

The independent Data Monitoring Committee (DMC) will require access to un-blinded data to ensure continued safety of the trial. The code break will be provided directly to the DMC by members of the Clinical Trials Unit operating the randomisation system who are independent of the trial.

